180 glucose and insulin sensitivity (HOMA-IR), at 3, 6 and 12 months between the vagus nerve
181 cryoablation group and the lifestyle intervention monotherapy group.
182

183 The primary safety endpoint of the trial is occurrence of death and all procedure related
184 complications, such as bleeding, infection, pneumothorax, hemothorax, pulmonary injury,
185 complications of sedation, pain requiring hospital admission or treatment, dysphagia,
186 gastroparesis, nausea and vomiting, and gastrointestinal ulceration for the duration of the study.
187

188 Secondary outcomes include differences between treatment groups in any of the following
189 measures:

- 190 1. Body mass index (BMI), waist circumference, and waist-to-hip ratio at 3 and 6 months
191 compared to baseline
- 192 2. Lipids (total cholesterol, LDL, triglycerides) at 6 months compared to baseline
- 193 3. Systolic and diastolic blood pressure at 3 and 6 months compared to baseline
- 194 4. Daily caloric intake as measured by 3-day food recall compared to baseline at 3 and 6
195 months.
- 196 5. Changes in antihyperglycemic medication regimen compared to baseline at 3 and 6
197 months.
- 198 6. Appetite, hunger and satiety scoring by visual analog scale at baseline, 1 week, 1 month,
199 3 months and 6 months
- 200 7. Physical activity questionnaire (IPAQ) at baseline, 3 and 6 months
- 201 8. Fasting glucose and insulin levels at 3 and 6 months compared to baseline

202 203 **C. STUDY DESIGN:**

204 This is a randomized, controlled, unblinded clinical study in obese adult patients with T2D,
205 HbA1c 7.5-10.5%, BMI 30-40 kg/m² treated with non-insulin antidiabetic medications with

207 stable doses for at least 3 months.

208 Subjects will be pre-screened with the relevant questions from the Three Factor Food
209 Questionnaire by phone or in person to determine eligibility prior to consent. Following consent
210 and screening for trial eligibility, subjects will be randomized to treatment group. The primary
211 endpoint, glycemic control, will be assessed at 6 months post-procedure. Patients will be
212 recruited from the diabetes clinic at Grady Memorial Hospital and Emory University Clinics.
213

[figure not shown]
214 We will be screen up to 40 participants to be able to randomized 30 patients, they will be
215 enrolled in this pilot exploratory study. Patients will be randomly allocated to undergo either CT

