245 be NPO for 12 hours prior to the ablation procedure. Metformin and sulfonylureas will be held
246 the evening prior to the procedure. Subjects will present to the Interventional Radiology pre-
247 procedure holding area at 8:00 AM on the morning of the procedure and will have a peripheral
248 IV placed by nursing staff. Point of care blood glucose level will be checked; the procedure will
249 be deferred for BG >250 mg/dl until diabetes control can be better optimized. Low doses of
250 sedation will be used with IV versed and fentanyl. An Interventional Radiology nurse will
251 monitor the subject while sedation is being administered. Skin will be numbed using lidocaine.
252 The procedure will be done under CT guidance and involves a 4-5 mm scalpel incision followed
253 by percutaneous probe placement about the posterior gastroesophageal junction (the location of
254 the posterior vagal trunk). The probe will create a zone of decreased temperature (-20 to -40°C)
255 involving the posterior vagal nerve fibers/plexus. The cryoablation process will include a 3-

256 minute freeze, followed by a 1-minute thaw, and a second 3-minute freeze and 1 minute thaw.
257 After the procedure, a sterile dressing will be applied, and subjects will be monitored for 12
258 hours.

259

260 **Lifestyle Intervention:** All subjects will receive standardized dietary and exercise counseling
261 from a registered dietitian and exercise physiologist ([name]). Participants will be counseled
262 to follow a low carbohydrate diet providing a moderate amount of carbohydrates per day (~100
263 g). Focus will be on increasing fruits and vegetables and decreasing refined sugars and processed
264 foods. Dietary counseling will include motivational interviewing, goal setting and nutrition
265 education.⁴⁴ Subjects will also be encouraged to slowly increase physical activity to at least 150
266 minutes weekly. The lifestyle intervention structure will include detailed counseling sessions at
267 baseline, 3 and 6 months. These sessions ideally will occur face-to-face, although telemedicine
268 visit (via zoom) will be permitted on case-by-case basis due to the COVID-19 pandemic. In
269 addition, there will be weekly phone calls or texts (participants' choice) providing a total of 26
270 points of contact recommended by the USPSTF (United States Preventive Services Task
271 Force).⁴⁵

272

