273 **Surveys:** Subjects will complete a number of surveys as part of participation in the trial. at
274 baseline, 3 months, 6 months and 12 months. Three-day food records are a validated method of
275 assess food intake⁴⁶ and will be administered at baseline, 3 months, 6 months and 12
276 months. Subjects will also complete visual analogue scale ratings of appetite at baseline, 1 week,
277 1 month, 3 month, 6 month and 12 month.⁴⁷ The International Physical Activity Questionnaires
278 (IPAQ) is to provide a set of well-developed instruments that can be used internationally to
279 obtain comparable estimates of physical activity.⁴⁸ Subjects will also complete the relevant
280 questions from the Three Factor Eating questionnaire during pre-screening and must have an
281 average score ≥ 3 on questions 4, 8, 9, 13, and 14 to be eligible. The entire questionnaire will be
282 administered after subjects have been consented. The Three Factor Eating Questionnaire is a
283 self-assessment scale used in studies of eating behavior in overweight and normal individuals,
284 designed to assess cognitive restraint, disinhibition, and hunger.⁴⁹ Preliminary investigation of
285 this cryovagotomy procedure has identified subjects who score ≥ 3 on the aforementioned
286 questions to be those who respond best to the intervention.¹⁶

287

288 **Blinding.** The trial design is an unblinded, randomized control trial. By nature of the study
289 design, participants and study personnel must be aware of which arm participants are enrolled.

290

291 E. POTENTIAL RISKS AND BENEFITS:

292 **Risk to Human Subjects:** Specific to this procedure, a 20 subject pilot was recently completed
293 that demonstrated no procedure related complications or adverse events during 6 months of
294 follow up. During the 12 month extension, 1/20 patients was found to have a prolonged gastric
295 emptying time, though it is unclear if this was related to the study procedures as no baseline
296 measurements were performed and the subject was asymptomatic. The Visual-Ice Cryoablation
297 System is intended for cryoablative tissue destruction using a minimally invasive procedure. As
298 described in the Icesphere 1.5 Needle user manual on page 14, there are no known adverse
299 events related to the specific use of the cryoablation needles⁵⁰. The procedure is CT guided

300 which allows for real-time visualization of the process to ensure efficacy and avoid damage to

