21. History of autonomic dysfunction, including amyloidosis, Parkinson's disease, autoimmune disease, spinal cord injury

G. STATISTICAL CONSIDERATIONS:

464 The primary outcome is the difference in glycemic control (as measured by HbA1c) at 6 and 12
465 months between the vagus nerve cryoablation group and the lifestyle intervention group.
466 Summary statistics including mean, median, and standard deviations for the changes in HbA1c
467 at 3, 6, 9 and 12 months will be computed. We will then compare the changes at 6 months
468 between the two treatment groups by a nonparametric Wilcoxon test or a two-sample t-tests
469 (with appropriate data transformation if needed). We will conduct one-way ANOVA to estimate
470 the mean difference in glycemic parameters at 6 and 12 months month between the two
471 treatment groups. We may further adjust for some important confounders by using linear
472 regression models. We will also assess the glycemic control outcomes simultaneously across
473 different follow-up visits (i.e. 12, 24 weeks) through repeated measures ANOVA models, which
474 appropriately account for within-subject correlations in the measurements. In addition, we will
475 consider repeated measures linear regression model with visits incorporated as a continuous time
476 variable. We may include other covariates in the model when feasible.

477 The primary safety endpoint of the trial is the occurrence of death and all procedure related
478 complications, such as bleeding, infection, pneumothorax, hemothorax, pulmonary injury,
479 complications of sedation, pain requiring hospital admission or treatment, dysphagia,
480 gastroparesis, nausea and vomiting, and gastrointestinal ulceration for the duration of the study.
481 We will first use the Chi-square test (or Fisher's exact test) to compare the occurrence of this
482 primary safety endpoint between the two treatment groups. We will perform logistic regression
483 to evaluate the group difference while adjusting for other potential confounders such as age,
484 gender, and BMI. In addition, we will compare the number of procedure related complications
485 by using Poisson regression or Negative Binomial regression between the two treatment groups.
486 Standard model selection (e.g. forward, backward variable selection) and model checking
487 procedures (e.g. deviance residual plot and Hosmer- Lemeshow test) will be performed to ensure
488 the adequacy of the final models.

489

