490 Secondary outcomes will be compared between the two treatment groups. For continuous
491 secondary outcomes, we will follow the plan proposed for primary outcome. For discrete
492 secondary outcomes, we will first conduct cross-sectional comparisons based on Chi-squared
493 tests or Fisher's exact test. If the discrete outcome is measured at multiple visits, we will fit
494 repeated measures generalized linear models to simultaneously assess the difference in the
495 longitudinal discrete outcome between the two treatment groups. Other covariates may be
496 included in the models if feasible.

497

498 **Sample Size Calculation and Power Analysis:**

499 This study is generating pilot data for utilization of this procedure in a novel patient population.
500 Given the 15 patients per group, taking into account 20% attrition rate, we would have 12
501 patients per group. In this case, we would have 80% power to detect a difference in glycemic
502 control outcome change that equals 1.2 times the standard deviation of the glycemic control
503 outcome change. The data generated from this study will provide useful relevant preliminary
504 data for planning larger randomized studies.

505

506

507

IV. DATA HANDLING AND RECORD KEEPING:

508 Data collection records with personal identifiers will be stored in locked file cabinets. Blood
509 samples drawn in conjunction with this study will not be labeled with information that could
510 directly identify study subjects. De-identified serum samples will be stored. We may use the
511 samples collected and stored in this study for future studies without a separate IRB consent for
512 the subjects. This will be explained to the study subjects at the time of consent. If we use the
513 samples in future studies, coded identifiers will be used. The informed consent will make it clear
514 that subjects can request their samples to be destroyed at any time. Presentation of the study
515 results at regional or scientific meetings or in publications will not identify subjects. Access to
516 research and confidential records will be limited to clinical investigators, research coordinators,
517 and the IRB at Emory University.
518

519 Study coordinators and/or investigators will collect baseline and follow up data, complete the
520 CRF (case report form) and enter data into RedCap (electronic database provided by the Emory
521 Research Information Technology Department). Baseline data will include demographics

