522 (gender, age, ethnicity), duration of diabetes, comorbid conditions, medications, BMI, screening
523 labs, QOL assessment scores, appetite score, three-day food records analyzed using Nutrition
524 Database System for Research (NDSR) and physical activity questionnaire (IPAQ).⁴⁸ Follow up
525 data will include medications, BMI, body measurements, follow-up labs, QOL assessment
526 scores, appetite score, three-day food record, IPAQ, and adverse events.
527
528

529 **V. ETHICS:**

530 **A. INFORMED CONSENT**

531 After identification of eligible patients these individuals will be provided basic information
532 regarding the study and, if interested, a member of the research staff using inclusion/exclusion
533 criteria delineated elsewhere in the protocol will then screen patients. Informed consent will be
534 obtained before any trial related procedures including screening procedures. The consent form,
535 potential risks and benefits, and the rights of research participants will be explained to the
536 participant by the investigators or research coordinator. Individuals will be asked if they have
537 questions, and a member of the research staff will answer questions. The principal investigator
538 (PI) will also be available at all times to answer questions that participants may have during the
539 consent procedure or during the time a participant is enrolled in the study. The consent form will
540 be completed only by trained research personnel familiar with the study protocol procedures,
541 informed consent process, who have undergone CITI training in accordance with the IRB
542 guidelines of Emory University. A signed copy of the consent form will be provided to the
543 participant and a copy will be placed in the file that is maintained for each participant in the
544 study office. Adults who speak any of the following languages (English, Spanish) will be
545 approached for participation in the study.
546
547

548 **B. RECRUITMENT AND RANDOMIZATION**

549 Subjects will be recruited from the Diabetes Clinic at Grady Memorial Hospital and Emory
550 Healthcare clinics. Patients with diabetes will be identified electronically. Once a potential
551 candidate is identified, we will approach the primary clinician as well as the patient for consent.

552

553 Patients will be randomized consecutively using a computer-generated randomization table
554 provided by [name] at the Emory School of Public Health.

555

556

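### The blinding statement exempts no study role, so food-record coding and the choice of efficacy analysis are left unmasked although the procedure does not require it

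*Combined protocol and SAP*

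**What the plan says.** Section III.C declares the design openly: "This is a randomized, controlled, unblinded clinical study in obese adult patients with T2D". The Blinding paragraph in III.D goes further. It gives the nature of the design as the reason why the two groups it names, participants and study personnel, have to know the allocation ("design, participants and study personnel must be aware of which arm participants are enrolled"). It lists no roles and makes no exceptions.

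Two parts of the plan depend on people to whom that reason may not apply.

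- **Caloric intake.** Section III.B lists as a secondary outcome "Daily caloric intake as measured by 3-day food recall compared to baseline at 3 and 6" months. Section III.D and section IV (Data Handling and Record Keeping) describe the instrument as a three-day food record. Section IV names the nutrition software used to process it ("labs, QOL assessment scores, appetite score, three-day food records analyzed using Nutrition") but not who does the coding, or whether that person knows the arm. On data collection in general it says "Study coordinators and/or investigators will collect baseline and follow up data, complete the" case report form.
- **Analysis.** Section III.G leaves several choices open for the HbA1c comparison: a Wilcoxon test or a t-test, a transformation if one is needed, and optional adjustment for confounders that are not named. Continuous secondary outcomes follow the same plan. The section does not mention masking.

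**The concern.** Open-label treatment and unmasked assessment are separate decisions, and the Blinding paragraph treats them as one. Percutaneous cryoablation cannot reasonably be hidden from the patient, the operator or the clinicians who manage the patient afterwards. Someone turning a written food record into calories, or choosing a regression model, does not need the allocation to do the job.

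Coding a food record takes judgement about portions, preparation and ambiguous entries. The trial expects the cryoablation arm to lose more weight, and its background section describes reduced appetite after the procedure. A coder who knows the arm could resolve doubtful entries in that direction without meaning to. Once in the database, such a shift looks the same as a treatment effect on intake and cannot be separated from it afterwards.

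The analysis is exposed differently. With the arm visible, the test, transformation or covariate set can be chosen after seeing which option favours which group. The results are meant to support a grant application and the planning of larger trials, so a distorted secondary result would carry forward.

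**Working it through.** **1. Does the stated reason reach each role?** The documents support the following comparison.

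| Role | What the documents say | Does the procedure require knowledge of the arm? |
|---|---|---|
| Patient | Undergoes the procedure or does not (III.D) | Yes |
| Operator and procedure-day team | Perform it and monitor the patient (III.D) | Yes |
| Treating clinicians | Adjust medication and ask about adverse events at visits (III.C) | Yes, in practice |
| Food-record coder | Not named; software only (IV) | No reason given |
| Analyst | Not named; no mention of masking (III.G) | No reason given |

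The word *must* is justified for the first three rows and not for the last two.

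**2. Reproduce the plan's own figure.** Inputs from the sample-size paragraph of III.G are 15 per group, 20% attrition and a detectable difference of 1.2 SD with 80% power. The documents state no alpha; two-sided 0.05 is assumed.

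- Evaluable per group: 15 × 0.80 = 12.
- Two-sample t-test: df = 2 × 12 − 2 = 22, critical value 2.074.
- Noncentrality: 1.2 × √(12/2) = 1.2 × 2.449 = 2.939.
- Power from the noncentral t: 80.2%, against the stated 80%. The figure reproduces.

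**3. Use the same method to illustrate a coding bias.** Suppose there is no true effect on intake, but coding differs systematically between arms by b SD of the change. The noncentrality is b × √(12/2), and the rejection rate is the probability that a noncentral t with 22 df lies beyond ±2.074.

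| Differential error b (assumed) | Noncentrality | False-positive rate |
|---|---|---|
| 0 | 0 | 5.0% |
| 0.10 SD | 0.245 | 5.6% |
| 0.20 SD | 0.490 | 7.6% |
| 0.30 SD | 0.735 | 10.8% |
| 0.40 SD | 0.980 | 15.5% |
| 0.50 SD | 1.225 | 21.6% |

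To put this in calories, assume an SD of change of 500 kcal/day. Then 90 kcal/day is 90/500 = 0.18 SD and gives 7.1%, and 180 kcal/day is 180/500 = 0.36 SD and gives 13.5%. The documents give neither an SD for intake nor any estimate of coding error. The table shows how sensitive a trial of this size is to such an error; it does not estimate what will happen.

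**4. The analysis choices.** No figure can be attached to these. The effect depends on which options would be tried and on how far their results differ, and the documents settle neither.

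**The case against.** The case for leaving the sentence alone has several parts.

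**The trial is a declared open-label pilot and the exposed outcome is secondary.** This is correct and limits the weight of the point. Of the primary outcome, III.G says: "The primary outcome is the difference in glycemic control (as measured by HbA1c) at 6 and 12" months. HbA1c is a laboratory value, as are fasting glucose and insulin.

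**Patient reporting may bias the food records more than coding does.** This also stands. Unblinded patients decide what to write, and masking the coder does not change that. Masked coding removes one source of error; it does not make caloric intake a sound comparison.

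**The sizes are assumed.** They are. No SD or error in the working, other than the plan's own 1.2 SD, comes from the documents.

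**The roles are not spelled out.** A reader might take the sentence to say that every member of staff, coder and analyst included, is told the arm. It contains no *all* and no list of roles. What can be said is that it exempts nobody, and that no other section provides masking for these two tasks.

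**Masking the measurements could need more people.** A reader might extend the point to waist and hip, since III.B lists "Body mass index (BMI), waist circumference, and waist-to-hip ratio at 3 and 6 months" and a tape reading involves judgement, and might suppose that masking it would be free. The documents do not support that. They give no staffing figures. The 3- and 6-month visits also include adverse-event questions, medication adjustment and counselling, so a measurer unaware of the arm could well be an additional person. This objection succeeds for the tape measurement. It does not reach record coding or arm labels, where relabelling files is enough.

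**Conclusion.** The point holds for food-record coding and for the choice of efficacy analysis. The stated reason for unmasking does not extend to these tasks, nothing else in the plan covers them, and masking them is cheap. The consequence is avoidable bias in one named secondary outcome, plus arm-informed freedom in choosing the efficacy models.

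The size cannot be determined from the documents. With 12 per arm and an assumed two-sided 5% test, differential coding errors of 0.10 to 0.50 SD would give false-positive rates of 5.6% to 21.6% for caloric intake, with 7.6% at 0.20 SD. Every error size in that range is an assumption.

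A reader might infer that the primary result is compromised by observer bias. The documents do not support this, because HbA1c is measured in the laboratory; the primary analysis is touched only through the open modelling choices. This is a worthwhile improvement to the protocol's wording and file handling. It is not a flaw that undermines the trial.

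**What to change.** Replace the sentence in the Blinding paragraph of III.D with a statement by role:

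> Patients, operators and treating clinicians know the arm. Food records carry only study ID and visit code when entered in the nutrition database. The choice of test, transformation and covariates for the efficacy outcomes is finalised on a dataset with masked arm labels.

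The last sentence is limited to efficacy because procedure-related complications would reveal the arm, so masked labels would mean little for the safety models.

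For waist and hip, add a written standard measuring procedure, and do not require a separate masked assessor.

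The cost is protocol wording and file relabelling; sample size, power and alpha do not change. One small weakness remains: the documents do not name the coder, and if that person also counsels patients, a record may sometimes be recognised. The trial report should still say that patients completed their food records knowing their arm.

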216 guided cryoablation of the vagus nerve plus lifestyle intervention or lifestyle intervention alone.

217 **Group 1:** CT guided cryoablation of the vagus nerve plus lifestyle intervention (n=15).

218 **Group 2:** Lifestyle intervention by trained RD/CDE (n=15).

219 All subjects will have the procedure performed at Grady Memorial Hospital or Emory University
220 Hospital Midtown or Johns Creek by trained study personnel.
221

222 The study schema is shown below. Both groups will undergo screening for eligibility followed
223 by randomization. If the subject is not fasting at time of initial consent and screening, he/she will
224 be brought back for a subsequent visit with fasting blood work. Subjects must be randomized
225 within 4 weeks of the screening visit. If the randomization visit falls outside of the 4 week time
226 frame, the subject must undergo repeat screening procedures. In- person lifestyle counseling will
227 be provided at baseline visit for both groups. Those undergoing cryoablation will receive a phone
228 call 24 hour post-procedure to evaluate for any immediate complications, 1 week in person
229 follow up visit, as well as a safety call at 2 months. Subjects in both groups will have weekly
230 contact with RD and in person follow up visits at 4 weeks, 3 months, and 6 months. Blood work,
231 anthropometric data and questionnaires will be administered at baseline, 3 months, and 6 months.
232 Safety follow up appointments will be scheduled at 9 months and 12 months, though no further
233 lifestyle counseling will be provided after 6 months. Questioning regarding adverse events and
234 side effects will occur at all visits, as well as assessment of glycemic control. Anti-
235 hyperglycemic medications will be adjusted at visits under the direction of the endocrinologist,
236 or as needed for clinically significant hypo- or hyperglycemic events.

237
238

239 Blood work will be as follows: For all lab parameters, subject results must be within the
240 reference range unless otherwise specified by inclusion/exclusion criteria or if assessed by study
241 physician to be not clinically significant.

Lab test	Baseline	3 months	6 months	9 months	12 months
Complete metabolic panel	X	X	X	X	X
Pregnancy test	X	X	X	X	
HbA1c	X	X	X	X	X
Lipid panel	X		X		
Insulin level	X	X	X		X
TSH	X				

242
243

D. STUDY PROCEDURE:

244 **Cryoablation procedure (to be performed by [name] or [name]):** Subjects will

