357 adjusted. Subjects on metformin will have the dose titrated to a maximum of 2000 mg/d if
358 tolerated. Sulfonylureas can be titrated to maximal doses per manufacturer instruction. Subjects
359 may be prescribed rescue therapy with insulin in the event of significant hyperglycemia
360 unresponsive to titration of oral agents. In the setting of BG <100 mg/dl, sulfonylurea doses will
361 be decreased by 50% and discontinued if necessary. If BG <55 mg/dl, sulfonylureas will be
362 stopped. Metformin will be stopped if hypoglycemia persists.

363

364 **Technical success rate of the procedure and procedure related complications:**
365 Discontinuation of the trial will occur if 3 participants within the first 8 of 30 planned experience
366 significant adverse events (AEs) (Grade 3 procedure-related AE or procedure-related serious
367 AE) at any point during follow-up and if 4 participants experience significant AEs (Grade 3
368 procedure-related serious AE) at any time. The trial will be stopped at any point if a Grade 4 or
369 Grade 5 AE occurs until determination can be made regarding its potential relationship to study
370 involvement.

371

372 **Grading of AEs:**

373

Grade 1	Mild; asymptomatic or mild symptoms; clinical or diagnostic observations only; intervention not indicated
Grade 2	Moderate; minimal, local or noninvasive intervention indicated; limiting age-appropriate instrumental ADL
Grade 3	Severe or medically significant but not immediately life-threatening; hospitalization or prolongation of hospitalization indicated; disabling; limiting self-care ADL
Grade 4	Life-threatening consequences; urgent intervention indicated
Grade 5	Death related to AE ⁶⁷

374

375 Specific clinical signs or symptoms that will qualify for the above criterial include (amongst
376 other potential Grade 3-5 AEs not listed here): constitutional symptoms (severe fatigue
377 interfering with ADLs, fever $> 40^{\circ}\text{C}$, prolonged and/or severe rigors), endocrine (uncontrolled
378 hyperglycemia, ketoacidosis), gastrointestinal (inadequate caloric intake requiring TPN or IV
379 fluids, diarrhea requiring IV fluids and/or manifesting as >7 stools/day, symptomatic abdominal
380 distention or bloating, severe abdominal pain requiring narcotics, ileus, severe nausea requiring
381 hospitalization, bowel obstruction or perforation), hemorrhage requiring intervention, infection
382 requiring antibiotics, or pain interfering with ADLs.

383

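### The early Grade 3 stopping limit counts the first 8 of 30 randomised, about half of whom never have the procedure, and the rule's two limits are worded inconsistently

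*Combined protocol and SAP*

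**What the plan says.** Section III.E, in the paragraph on technical success and procedure-related complications, opens: "Discontinuation of the trial will occur if 3 participants within the first 8 of 30 planned experience" "significant adverse events (AEs) (Grade 3 procedure-related AE or procedure-related serious" "AE) at any point during follow-up and if 4 participants experience significant AEs (Grade 3" "procedure-related serious AE) at any time. The trial will be stopped at any point if a Grade 4 or" Grade 5 event occurs, until its relation to the study has been judged. There are thus two Grade 3 count limits and a separate hold for Grade 4 or 5.

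Section III.C fixes what the 30 means: "We will be screen up to 40 participants to be able to randomized 30 patients, they will be" enrolled in the pilot. Group 1 is "CT guided cryoablation of the vagus nerve plus lifestyle intervention (n=15"), and Group 2 is 15 participants with lifestyle intervention only. A later sentence in III.C about where all subjects have the procedure concerns location and does not give Group 2 a procedure.

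Section V.B says that allocation follows a computer-generated table. It does not mention blocking.

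The plan gives no tolerable event rate and no stopping probability for the rule.

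**The concern.** Three features of the paragraph do not fit together.

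- **Denominator.** The events counted are procedure-related, but the window of 8 is drawn from both arms. Control participants have no procedure and cannot contribute an event.
- **Definition.** The first limit counts a procedure-related event that is Grade 3 or serious. The second, read literally, counts only one that is both. A non-serious Grade 3 event would then count toward one limit and not the other. Such events are plausible, because the examples of qualifying Grade 3 to 5 events include infection "requiring antibiotics, or pain interfering with ADLs", neither of which need involve admission.
- **Connective.** The limits are joined by "and if". Taken literally, both must be met.

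This is the only numerical limit on Grade 3 events for an invasive procedure in a new patient population. The early limit is there to stop before more people are exposed. If investigators and the DSMC read the paragraph differently, they could disagree on whether the trial must stop.

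**Working it through.** The plan has no figure of its own for this rule to reproduce, so the check is an exact enumeration.

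**Inputs from the protocol.** 30 randomised, 15 to cryoablation (III.C); early limit 3 within the first 8; later limit 4 at any time (III.E).

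**Assumption.** p is the true probability that a cryoablated participant has a significant event. The protocol does not give it, but offers two partial anchors:

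- The procedural risks listed in III.E are below 2, 1, 0.5 and 1%, which sum to below 4.5%. That list omits later effects such as gastroparesis.
- The pilot reported 0 of 20 complications, in non-diabetic subjects. The exact one-sided 95% upper bound is 1 − 0.05^(1/20) = 13.9%.

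Rates of 20% and 30% lie beyond both anchors and are shown for contrast.

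**Step 1: number treated among the first 8 (K).** The expected value is 8 × 15/30 = 4. If K is 2 or less, the early limit cannot be met. That chance depends on the unstated randomisation method:

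- Blocks of 2 or 4: K = 4 exactly, so 0%.
- Single permuted 15/15 list: P(K = k) = C(15,k)·C(15,8−k)/C(30,8), so P(K ≤ 2) = (6,435 + 96,525 + 525,525)/5,852,925 = 10.7%.
- Simple randomisation: P(K ≤ 2) = (1 + 8 + 28)/256 = 14.5%.

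**Step 2: chance that the early limit is met.** This is the sum over k of P(K = k) × P(Bin(k,p) ≥ 3). For the corrected window, K = 8.

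| p | As written, single list | As written, K = 4 | First 8 cryoablated |
|---|---|---|---|
| 10% | 0.5% | 0.4% | 3.8% |
| 13.9% | 1.3% | 1.0% | 8.8% |
| 20% | 3.6% | 2.7% | 20.3% |
| 30% | 10.0% | 8.4% | 44.8% |

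For example, with K = 4 and p = 20%: 4 × 0.2³ × 0.8 + 0.2⁴ = 0.0272.

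**Step 3: chance that the trial stops on either limit, one definition.** Stop if 3 or more events occur among the K, or 4 or more among all 15 treated.

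| p | 4-of-15 limit alone | Either limit, as written (single list) | Either limit, first 8 cryoablated | Gain (points) |
|---|---|---|---|---|
| 4.5% | 0.4% | 0.41% | 0.67% | 0.3 |
| 10% | 5.6% | 5.7% | 7.1% | 1.4 |
| 13.9% | 14.5% | 14.8% | 17.0% | 2.2 |
| 20% | 35.2% | 35.5% | 38.3% | 2.7 |
| 30% | 70.3% | 70.5% | 72.4% | 1.9 |

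As written, the early limit adds at most about 0.35 points to the 4-participant limit (35.53% against 35.18% at p = 20%).

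**Step 4: "and if" taken literally.** If both limits must be met (single list, one definition), the chance of stopping at 10, 20 and 30% is 0.4, 3.2 and 9.8%, against 5.7, 35.5 and 70.5% when either suffices.

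**The case against.** The strongest reply is that the denominator hardly affects whether the trial stops. The 4-participant limit does nearly all the work, and the gain from correction is under 3 points at every rate examined and about 0.3 points at the protocol's own listed risks. The wide contrasts in the early limit appear at rates above what the pilot suggests. All of this stands.

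It is also fair that "and if", with its repeated "if", reads naturally as two triggers, and that the second definition may be shorthand for the first, since both carry the same label. A broad early screen with a narrower whole-trial limit would be a coherent choice too. The Grade 3 description includes "hospitalization or prolongation of hospitalization indicated; disabling; limiting self-care ADL", so overlap between Grade 3 and serious events could be high.

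Other safeguards are substantial. A Grade 4 or 5 event halts the trial. All adverse events go to the IRB, the monitoring board and the FDA. The DSMC reviews unblinded safety data every 6 months, and as needed for an unanticipated adverse device effect, and can recommend stopping. None of these supplies a Grade 3 count, however, and no other section settles the denominator, the definition or the connective.

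A reader might go further and infer that the narrower second definition sharply cuts the chance of stopping. If 90% or 50% of first-limit events also met the second, stopping at a 20% rate would fall from 35.5% to 28.6% or 8.3%. Those shares are pure assumptions. The documents give no overlap, so these figures illustrate sensitivity and do not measure a defect.

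**Conclusion.** The rule is wrong as written on the denominator and ambiguous on the definition and the connective. The early limit works at about 3 of 4 treated participants, where its wording suggests 3 of 8. It has roughly one seventh (10% rate) to under one quarter (30% rate) of the chance of being met that it would have over the first 8 cryoablated. Depending on the randomisation method, there is a 0 to 14.5% chance that it cannot be met at all.

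A reader might infer that an unsafe trial would therefore run on unchecked. The documents do not support that. With alternative triggers and one definition, overall stopping is almost unchanged, and the loss is confined to the early check. How much calendar time or extra exposure that costs is unknown: accrual was not modelled, and early-cohort events count at any point in follow-up. The literal "and" would reduce stopping greatly, but it is probably not what was meant.

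The textual points are certain. The probabilities rest on assumed event rates, independent events, 15 participants actually cryoablated and, for the as-written figures, a single permuted list unless stated otherwise. This should be fixed because it is a safety rule and the repair is cheap.

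**What to change.** Reword the paragraph in III.E so that the trial stops if EITHER 3 of the first 8 participants who undergo cryoablation OR 4 cryoablated participants at any time have a significant adverse event. Define that term once for both limits. The sponsor and the DSMC should choose the definition:

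- The broader one (Grade 3 or serious) protects more, but lets four non-serious events end a small pilot.
- The narrower one (Grade 3 and serious) stops less often.

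Keep the Grade 4/5 hold unchanged. The thresholds of 3 and 4 are not in question here.

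The cost is one reworded paragraph, one decision, and IRB and FDA review of the revised rule. No extra participants or visits are needed. The downside is a slightly higher chance of stopping: 7.1% against 5.7% at an assumed 10% rate, if one definition and two alternative triggers were always intended. The rise would be larger if the narrower definition or the literal "and" had been meant.
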